6.3. Prior and Concomitant Medications

Medications will be coded according to the World Health Organization (WHO) Drug Dictionary (version V2016.01). Medications reported on the case report form (CRF) will be categorized for analysis as prior, concomitant, or post-treatment by comparing the medication start and stop dates with the first and last dose dates of study treatment. Medications that the participant had taken from 12 weeks prior enrollment through the end of study participation were recorded in the CRF. Prior medications will have both the medication start and stop dates prior to the date of the first dose of study treatment. Post-treatment medications will have the medication start date after the date of the last dose of study treatment. All other medications will be classified as concomitant, indicating that use of the medication overlapped with use of the study treatment by at least one day.

A listing of all medications reported in all participants in the safety population by treatment arm will be prepared.

6.4. Medical History

Medical histories are captured at screening for all randomized participants in the Medical History CRF. Body systems classified as abnormal in the Medical History CRF will be listed by treatment arm for all participants in the safety population.

7. STUDY OPERATIONS

7.1. Protocol Deviations

Major protocol deviations occurring throughout the duration of the study are captured on the Protocol Deviations CRF.

Major protocol deviations will be summarized and listed. The deviations will be summarized by whether the deviation was site-level or participant-level and by type of deviation:

- IRB Approval/Regulatory
- Informed Consent
- Entry Criteria Violations
- Study Treatment or Study Drug Related
- Protocol Mandated Concurrent Therapy Related
- Adverse Event/Serious Adverse Event Reporting Procedures
- Assessments and Laboratory Procedures
- Blind Break

The deviations will be listed by site, site-level deviations and participant level deviations, and by date of occurrence.

7.2. Randomization

Participants were randomized in a 1:1 ratio to either HCQ or placebo. Anticipating that some study sites would only randomize a few participants, an adaptive randomization procedure based on Pocock and Simon [1] minimization concepts was used to increase the likelihood of balance between treatment arms on key factors associated with progression to clinically-apparent RA. The factors used in the adaptive randomization procedure were smoker status (smoker vs. non-smoker), study site, and method of recruitment (i.e., first degree relative (FDR), general population, or clinic patient). Participants with elevated anti-CCP levels that met assay positivity criteria were identified for this trial through three general approaches that included the following:

- Pre-screening FDRs of patients with RA.
- Health-fair, biobank, or other population-based pre-screening.
- Identification in rheumatology clinics of participants with ACPA positivity in the absence of IA.

These three participant pools provided a sampling of the types of participants for whom this preventative approach would be applicable.

To avoid possible issues of familial correlation, our strong preference was to randomize only 1 FDR per family. Participants were asked about participation of immediate family members during the consent process and during study participation. However, recognizing operational

Autoimmunity Centers of Excellence
Statistical Analysis Plan – ARA08 StopRA

barriers to accurately track family membership and our suspicion that multiples per family would be a rare occurrence, randomization of multiple FDRs per family was allowed.

7.3. Blinding

Clinical staff were blinded to the treatment assignments until completion of the study with the exception of an unblinded pharmacist. In addition, clinical staff members, including the investigators, did not have access to any mechanistic data, and mechanistic laboratory staff did not have access to any clinical results until completion of the study.

No participant treatment assignments were unblinded prior to the end of the study.

7.4. Measures of Treatment Compliance

Both the investigational drug that was used during the course of the study, as well as any remaining unused investigational drug, were required to be accounted for on a drug accountability record provided or approved by the study sponsor or its designee.

Study participants received 1-2 pills of either HCQ or 1-2 pills of placebo for 12 months with dosing based upon Screening IBW as outlined in Table 2.

Table 2: Weight-based dosing regimen for HCQ (and placebo)

Weight (kilograms based on IBW*)	Number of pills**
≤ 24.4 kg (ideal or actual body weight)	Excluded from trial
> 24.4 - < 47 kg	1 pill daily
≥ 47 kg	2 pills daily

*IBW based on the following calculation:

Males: IBW = 50 kg + 2.3 kg for each inch over 5 feet, or subtract 1kg for every inch under 5 feet.

Females: IBW = 45.5 kg + 2.3 kg for each inch over 5 feet, or subtract 1kg for every inch under 5 feet.

** Each 200 mg HCQ pill contains 155 mg of active drug

Study therapy was dispensed per the schedule in Table 3.

Table 3: Study Therapy Distribution

Participant IBW at Screening	Baseline	Week 6	Week 12	Week 24	Week 36
> 24.4 - < 47 kg	1 bottle	2 bottles	2 bottles	2 bottles	3 bottles
≥ 47kg	2 bottles	3 bottles	4 bottles	4 bottles	6 bottles

Each bottle of study medication dispensed was recorded on the Study Drug Accounting Log CRF, along with the date the bottle was dispensed, the date the bottle was returned, the number of pills returned, and the number of pills lost.

Autoimmunity Centers of Excellence
Statistical Analysis Plan – ARA08 StopRA

The number of pills taken from each bottle will be computed as the number of pills in the bottle (i.e., 50) minus any pills lost or returned. The total number of pills expected to be taken will be calculated as the participant's treatment period duration (treatment end date – treatment start date + 1) multiplied by the number of pills the participant was expected to take each day (1 pill or 2 pills) based on the participant's Screening IBW.

For bottles that were not returned to the site, the total number of pills expected will be imputed from the date the bottle was dispensed until the date the next study drug bottle is dispensed, or until the participant's treatment discontinuation date, whichever occurs earlier. The total number of pills taken will be imputed under 2 scenarios:

- Case 1 (best): the number of pills taken is assumed to equal the number expected,
- Case 2: the number of pills taken is assumed to equal 50 (all pills in bottle).

Percent treatment compliance for each participant will be calculated as:

$$\% \text{ Compliance} = \frac{\text{Total number of pills taken}}{\text{Total number of pills expected}} \times 100$$

Compliance for individuals who failed to return bottles will be reviewed by the masked data review committee for exclusion from the PP population.

Study drug dosing will be listed by participant, visit and bottle. Information will include the date of dispense and return, number of pills returned, and number of pills lost.

8. EFFICACY EVALUATIONS

8.1. Overview of Efficacy Analysis Methods

8.1.1. Multicenter Studies

Study participants were consented at 15 study sites. The analyses of survival estimates at fixed points in time will not be stratified. Site and method of recruitment will be considered as possible fixed covariates in models for secondary efficacy analyses. All safety analyses will be based on pooled data with no adjustment or stratification.

8.1.2. Assessment Time Windows

Visit windows for each scheduled visit are provided in Table 4. The Baseline visit must be performed within 30 days of the Screening visit.

Table 4: Visit Target Days and Windows for Scheduled Visits

Visits	Target Day	Visit Type	Window
Baseline	0	Clinic	≤30 days from Screening
Week 6	42	Clinic	±7 days from target
Week 12	84	Clinic	
Week 18	126	Telephone	
Week 24	168	Clinic	
Week 30	210	Telephone	
Week 36	252	Clinic	
Week 42	294	Telephone	
Week 52	364	Clinic	±14 days from target
Month 15	457	Telephone	
Month 18	548	Clinic	
Month 21	639	Telephone	
Month 24	731	Clinic	
Month 27	822	Telephone	
Month 30	913	Clinic	
Month 33	1004	Telephone	
Month 36	1096	Clinic	

Data collected outside of the visit window will not be removed from analyses categorized by visit and will be included in analyses where time is a continuous variable.

8.1.3. Timing of Analyses

Final analyses for all endpoints will be conducted after participants have completed study participation and all data collected are locked.

8.1.4. Multiple Comparisons/Multiplicity

This study has a single primary analysis to be tested at $\alpha=0.05$. Consequently, no adjustments for multiplicity are needed for Type I error protection.

The secondary efficacy analyses are considered to be supportive with p-values and confidence intervals presented as descriptive measures of strength of evidence rather than formal statistical inference. Therefore, no multiplicity adjustments are needed for this study.

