same for both groups (i.e. 50% for both arms), then chance of triggering the futility criterion is 62%. On the other hand, if the design assumptions are correct (50% risk for placebo, 25% for HCQ), then the chance of triggering the futility criterion is 2%, and power is 82%. In addition, up to 3 interim analyses may be conducted to stop the study early for overwhelming evidence of efficacy provided the overall power for the primary endpoint analysis is maintained at greater than 80%. For example, under the design assumptions in Section 8.1, *Sample Size and Power*, and assuming enrollment is stopped at 4.5 years with 140 independent subjects (i.e. no other family members participating), and 20% loss over 3 years of follow-up (i.e. exponential loss), a simulation study using an O'Brien-Fleming alpha-spending rule showed that power would be 82% with 2 interim analyses at 4.75 and 5.75 years compared to 83% power with no interim analyses.

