11.5 Study Termination

In the event that the study is discontinued, sites will immediately notify subjects to terminate study agent and return for a close-out visit to the site within 30 days.

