5.4. Per Protocol Population

The Per Protocol (PP) population will be defined as those participants in the mITT population who receive at least 80% of the assigned study treatment regimen with no substantive deviations from protocol procedures that would impact evaluation of efficacy.

A data review panel that will include the Protocol Chair ([name]) and participants from DAIT and Rho, Inc., will evaluate deviations from the protocol including, for example, violations of entry criteria, departures from assigned treatment regimen, use of prohibited therapy or HCQ prescribed outside of the study, failure to complete study visits, or to complete visits within the specified visit windows. The participant ID numbers will be replaced with randomly generated ID numbers for the PP population review.

The ARA08 study conducted an interim analysis in April 2022 as part of the regularly scheduled DSMB review. The Interim Statistical Analysis Plan is provided in Appendix 14.1. Due to the evidence of futility in the interim analysis results, the DSMB recommended that the ARA08 study stop early, and that the treatment assignments be released to the participants. Since the ARA08 study treatment assignments will be unmasked prior to database lock, the data review panel evaluation of the participants to include and exclude from the PP population will take place after the treatment assignments have been unmasked.

Levels of HCQ analyzed from serum samples taken during the study treatment period will not be used in the masked data review panel's evaluations of deviations from the protocol. The panel may exclude participants from the PP population if protocol deviations would be expected to impact the primary efficacy endpoint. Primary and secondary efficacy analyses may be replicated on the PP population.

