11. INTERIM ANALYSES AND DATA MONITORING

11.1. Interim Analysis of the Primary Objective

The details for the planned interim analyses are provided in the ARA08 Interim Statistical Analysis Plan, which was finalized as version 1.0 on December 17, 2021. The ARA08 Interim Statistical Analysis Plan is included as Appendix 14.1.

The first interim analysis was conducted in April 2022, and the results of the interim analysis, “Interim Analysis for the April 2022 DSMB”, were included as an appendix in the closed report to the Data and Safety Monitoring Board on April 6, 2022 as part of the regularly scheduled review of the ARA08 study.

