5.2.2.1. Efficacy

The analysis will be based on the KM estimated risk of clinically-apparent RA at 36 months, where risk = (1-KM estimated probability of “survival”). Survival for this analysis is defined as absence of clinically-apparent RA. Estimated risks will be derived from a Kaplan-Meier curve using censored time-to-event data to account for attrition under the assumption of non-informative censoring.

The test statistic will be a Wald-type chi-square statistic derived by dividing the difference of the logit-transformed KM survival estimates for each arm by the associated variance derived using the delta-method. This analysis will ignore stratification by site and method of recruitment, because the unstratified test statistic has been shown to have better test performance (Klein, et al. 2007)

The test statistic at each interim analysis stage will be calculated as the logit transformed test statistic in Klein et al (X_{5k}^2):

$$X_{5k}^2 = \frac{\left[\log \frac{\widehat{S}_{Hk}(t_{36})}{1 - \widehat{S}_{Hk}(t_{36})} - \log \frac{\widehat{S}_{Pk}(t_{36})}{1 - \widehat{S}_{Pk}(t_{36})} \right]^2}{\frac{\widehat{\sigma}_{Hk}^2(t_{36})}{\left[1 - \widehat{S}_{Hk}(t_{36}) \right]^2} + \frac{\widehat{\sigma}_{Pk}^2(t_{36})}{\left[1 - \widehat{S}_{Pk}(t_{36}) \right]^2}}$$

where:

X_{5k}^2 = Test statistic at interim analysis stage k, k = 1 to 2

$\widehat{S}_{Hk}(t_{36})$ = KM estimated probability of RA-free survival in the HCQ treatment arm at month 36 for interim analysis stage k

$\widehat{S}_{Pk}(t_{36})$ = KM estimated probability of RA-free survival in the placebo treatment arm at month 36 for interim analysis stage k

$\widehat{\sigma}_{Hk}^2(t_{36})$ = Estimated variance of KM estimated probability of RA-free survival in the HCQ treatment arm at month 36 for interim analysis stage k, calculated via Greenwood's formula

$\widehat{\sigma}_{Pk}^2(t_{36})$ = Estimated variance of KM estimated probability of RA-free survival in the placebo treatment arm at month 36 for interim analysis stage k, calculated via Greenwood's formula

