The criteria at each interim analysis stage k to determine if the primary null hypothesis should be rejected will be determined by O'Brien-Fleming (OBF) boundary values for the standardized Z scores (Z_{OBFk}). PROC SEQDESIGN will be used to calculate the OBF boundary criteria using information levels based on the proportion of the maximum person-time accumulated on the date of data snapshot for the planned DSMB meeting. Enrollment closed on November 1, 2021 with 144 participants randomized to the study. Hence, the maximum person-years for the study is 144 participants * 3 years = 432 person-years. On the date of the data snapshot, we will compute the information fraction as the sum of time accrued from the day of randomization over all individuals divided by 432. Person-time for individuals randomized more than 3 years prior to the date of the data snapshot will be set at 3.0 person-years. In the example below, we are assuming data snapshot dates of 01FEB2022 and 01FEB2023 for the spring 2022 and spring 2023 DSMB meetings, respectively. Based on the study progress of all randomized participants, the information proportions for each interim analysis stage would be as follows:

Table 3: Estimated Information

Interim Analysis Stage (k)	Time Point	Elapsed Study Time (years)	Elapsed Study Time (person-years)	Estimated Information Proportion (I_k)
1	Spring 2022 DSMB [01FEB2022]	5.8	366.5	0.848
2	Spring 2023 DSMB [01FEB2023]	6.8	405.4	0.938
Final	End of Study [01NOV2024]	8.5	432.0	1.000

Note the actual information proportions will vary depending on the information available on the dates of data cuts.

At each interim analysis stage k , the primary hypothesis will be tested as follows:

- If $X_{5k}^2 \geq (Z_{OBFk})^2$, the null hypothesis H_0 that the RA-free survival at 3 years (36 months) is equal across arms is rejected, indicating there is strong evidence of a treatment effect.
- If $X_{5k}^2 < (Z_{OBFk})^2$, the null hypothesis H_0 that the RA-free survival at 3 years (36 months) is equal across arms is not rejected.

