8. APPENDICES

8.1. Power Estimates

Enrollment for the study will end November 1, 2021, regardless of the number of randomized participants accrued. Hence, the final number randomized will be known at the time of the first interim analysis. We computed power estimates for the following scenarios:

- Assume at the first interim that we will randomize 150, and final sample size = 150
- Assume at the first interim that we will randomize 150, and final sample size = 140

Table A1 presents power estimates for various combinations of RA-free survival rates for the placebo arm (45%, 50%, 55%) and the HCQ arm (70%, 75%, 80%). Based on prior information, the 50% vs 75% scenario represents a reasonable expectation. For the power estimates in Table A1, we simulated 10,000 trials under the following assumptions:

- Enrollment time of 5.5 years since study initiation
- 2 interim analyses conducted at 5.75 years and 6.75 years after study initiation
- Information proportions are calculated from the person-years estimates of study time since randomization, to a maximum of 3.0 years per participant, regardless of disease status or disposition, for each simulation sample
- LPLV at 8.5 years after study initiation
- Early Terminations/Lost to Follow-up participants: 20% in each treatment arm

The estimated overall power of the study equals the percent of simulated trials where the null hypothesis was rejected at an interim analysis or at the final end-of-study analysis.

Table A1: Overall Power Estimates for Various RA-Free Survival Rates

Final Sample Size	RA-Free Survival for Placebo	RA-Free Survival for HCQ		
		70%	75%	80%
150	45%	82.7%	94.4%	98.8%
	50%	64.8%	84.3%	95.7%
	55%	42.1%	66.9%	86.7%
140	45%	79.8%	92.9%	98.2%
	50%	60.6%	81.2%	94.3%
	55%	39.2%	63.2%	84.7%

Under the null hypothesis case (RA-free survival for both treatment arms at 50%), we estimated the following Type I error rates (95% CI), and they are statistically consistent with 5%:

- Final sample size = 150: 5.4% (5.0%, 5.8%)
- Final sample size = 140: 5.0% (4.6%, 5.4%)

Table A2 shows simulation results for the probability of meeting the futility criteria (Z-score < 0.3).

Table A2: Probability of Finding Futility (Z-score<0.3)

Final Sample Size	Interim Analysis	RA-Free Survival for Placebo/HCQ	
		50%/75%	50%/50%
150	1st	1.2%	62.1%
	2nd	0.5%	62.1%
140	1st	1.5%	61.4%
	2nd	0.9%	60.9%

Autoimmunity Centers of Excellence
Statistical Analysis Plan – ARA08 StopRA

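### SAP 8.1.4 waives Type I adjustment for the primary test without pointing to the interim O'Brien-Fleming boundaries in Appendix 14.1, and no final critical value is stated

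*SAP*

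**What the plan says.** SAP 8.1.4 sets one primary analysis at alpha 0.05 and concludes: "Consequently, no adjustments for multiplicity are needed for Type I error protection". Protocol 8.5.3 says the same. Neither section mentions interim testing.

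Appendix 14.1 (the interim SAP) states one pair of hypotheses for both the interim and the end-of-study analyses (section 5.2.1). In section 5.2.2.1, "The criteria at each interim analysis stage k to determine if the primary null hypothesis should be rejected will be determined by" O'Brien-Fleming boundary values. The statistic is defined as "Test statistic at interim analysis stage k, k = 1 to 2". Table 3 there has a final row at information 1.000 but no boundary. SAP Table 7, the primary estimand, gives 95% intervals and no critical value.

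Sequential control was planned. Protocol 8.4 describes a simulation in which an O'Brien-Fleming "alpha-spending rule showed that power would be 82% with 2 interim analyses at 4.75 and 5.75 years". Interim SAP Appendix 8.1 counts a trial as positive when the "null hypothesis was rejected at an interim analysis or at the final end-of-study analysis".

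On what happened, SAP 11.1 says: "The first interim analysis was conducted in April 2022". SAP 5.4 adds: "Due to the evidence of futility in the interim analysis results, the DSMB recommended that the ARA08 study stop early".

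**The concern.** A plan that may reject the null at an interim look spends part of its alpha there, so the final test must use a somewhat stricter threshold to keep 5% overall. A reader who follows 8.1.4 alone would use 1.96. A reader who follows Appendix 14.1 would use a larger value, but would have to derive it from an information fraction and a boundary form that the SAP does not settle. At stake are the two-sided level that the report attaches to the primary test, including a possible finding against HCQ, and the coverage of the 95% interval in Table 7.

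**Working it through.** **Inputs.** Overall two-sided alpha is 0.05 (SAP 8.1.4; protocol 8.3.1.1 for sidedness). Interim SAP Table 3 gives 144 x 3 = 432 person-years, 366.5/432 = 0.848, 405.4/432 = 0.938 and a final 1.000. Interim SAP Appendix 8.1 gives enrolment over 5.5 years, looks at 5.75 and 6.75 years, last visit at 8.5 years and 20% loss per arm.

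**Assumptions.** The correlation between looks is sqrt(t1/t2). The exact O'Brien-Fleming form is not stated, so I used the classical form and the Lan-DeMets spending form, the latter applied per side or to the two-sided level.

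**1. Reproducing the appendix's figures.** With uniform accrual (assumed), expected information is:
- at 5.75 years: 2.75/5.5 + (2.75/5.5)(1.625/3) = 0.771
- at 6.75 years: 3.75/5.5 + (1.75/5.5)(2.125/3) = 0.907

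I simulated 40,000 trials per scenario with exponential event and loss times and the logit Kaplan-Meier Wald test. The ranges cover the three boundary forms.

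| | Stated | Adjusted final boundary (2.06-2.11) | Final 1.96 |
|---|---|---|---|
| Power, n=150 | 84.3% | 83.8-84.4% | 86.3-86.5% |
| Power, n=140 | 81.2% | 80.8-81.4% | 83.4-83.7% |
| Type I, n=150 | 5.4% (5.0-5.8%) | 5.3-5.4% | 6.1-6.5% |
| Type I, n=140 | 5.0% (4.6-5.4%) | 5.1-5.2% | 5.9-6.2% |

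Both rows of the appendix fit an adjusted final boundary, and neither fits 1.96. Allowing for simulation error and settings that the appendix does not give, a final 1.96 in this design gives about 5.7-6.7%.

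**2. Two planned looks, large-sample theory.** The overall level is 1 - P(|Z1| < c1, |Z2| < c2, |Z3| < 1.96) at 0.848, 0.938 and 1.000:
- classical (2.235, 2.125): 5.73%
- Lan-DeMets per side (2.172, 2.13): 5.88%
- Lan-DeMets two-sided (2.128, 2.139): 6.01%

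**3. One look at 0.848.** The first-look boundary is 2.235 (three-stage classical), 2.199 (two-stage classical), 2.172 or 2.128 (the two Lan-DeMets forms), spending 0.0254 to 0.0333.

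Final information is not reported. Interpolating Table 3 linearly (405.4 - 366.5 = 38.9 person-years in 365 days from 1 February 2022):
- 6 April 2022: (366.5 + 38.9 x 64/365)/432 = 0.864
- 30 days later: (366.5 + 38.9 x 94/365)/432 = 0.872. Protocol 11.5 has participants "return for a close-out visit to the site within 30 days" if the study is discontinued.
- 1 August 2022: (366.5 + 38.9 x 181/365)/432 = 0.893

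I take 0.87-0.90 as an assumption.

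| Final information | Overall level with final 1.96 | Final p threshold for 5% overall |
|---|---|---|
| 0.87 | 5.02-5.12% | 0.0487-0.0498 |
| 0.90 | 5.13-5.34% | 0.0458-0.0485 |
| 1.00 | 5.49-5.85% | 0.039-0.044 |

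**4. After the futility criterion.** Under the null, P(Z1 < 0.3) = 0.618. Given Z1 < 0.3, the chance that the final test favours HCQ at 1.96 is about 4e-14 at final information 0.90 and 4e-7 at 1.00. The chance that it goes against HCQ is 0.025/0.618 = 4.0%.

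**The case against.** The strongest reply is that 8.1.4 concerns endpoints. It sits under a multiple-comparisons heading and reasons from one primary analysis and supportive secondary ones. Sequential testing has its own place in SAP section 11, which brings in Appendix 14.1, and 0.05 as the overall level is what an O'Brien-Fleming plan uses. On that reading the two texts are compatible, and leaving the final number unprinted is normal when information depends on the data cut. Much of this stands. What remains is that the wording of 8.1.4 is not limited to endpoints, it has no cross-reference, and the rejection rule as written stops at the interim stages.

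A reader might infer that the trial left its Type I error uncontrolled, or that the final test will be run at 1.96. The documents support neither: the protocol names a spending rule, the appendix's simulated error fits an adjusted boundary, and no section prints 1.96.

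A reader might also take 5.0-5.3% as the trial's real error rate. It is an illustration only. It treats final information as fixed, although the early finish followed from the interim result, and it uses person-time as a proxy for information on 36-month survival.

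Finally, SAP 5.4 says assignments are unmasked before database lock, so a critical value added now is not blinded prespecification. That limits the remedy to clear reporting.

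**Conclusion.** The point holds as a minor one: a missing cross-reference and an unstated final critical value. Followed literally, 8.1.4 does not deliver 5% overall. The excess is at most about one percentage point in large-sample theory with the two planned looks, somewhat more in simulation, and a few tenths of a point or less at the information that the stopped trial plausibly reached. The wording gap is certain. The sizes depend on the assumed boundary form, the projected first-look information of 0.848 and the interpolated final information.

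That the efficacy boundary was applied in April 2022 is inferred from the interim SAP; the closed report is not available and the observed Z is not given. If Z < 0.3 was met, a false claim of HCQ benefit is practically impossible, and only the nominal two-sided level and the interval coverage are affected.

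**What to change.** In SAP 8.1.4, state that 0.05 is the overall two-sided level for the primary test across the April 2022 look and the final analysis, and refer to Appendix 14.1. Report the information fraction and boundary used in April 2022, and give the final critical value computed from that look and the actual final information. Alternatively, state that after the futility stop the final primary p-value and 95% interval are descriptive. Matching the confidence level in Table 7 to the boundary is optional.

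The cost is a few sentences and one boundary calculation. At final information 0.87-0.90 the p threshold would move from 0.05 to about 0.046-0.050. The test statistic and sample size do not change. Under the descriptive option no analysis changes, and no confirmatory claim is made in either direction.
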